vnarimantal	(Scheduling Window)	
vnarimental		
ession 2 Visit 10)	8 hours + overnight/ 3 to 5 weeks after Experimental Session 1 (V5); at least 2 weeks after Integrative Session 1.3 (V9)  21 to 35 days after Experimental Session 1 (V5)  At least 14 days after Integrative Session 1.2 (V7); after Therapist Supervision Moeting	3 to 5 weeks after V5, and 2 weeks after Integrative Session 1.1 (V6). The second Experimental Session lasts 8 hours with an overnight stay. Dose is 80 or 120 mg plus supplemental half-dose (80 mg + supplemental 40 mg -OR- 120 mg + supplemental 60 mg) unless tolerability issues emerge with the first dose or the participant declines. Negative pregnancy test and drug test must be confirmed prior to dosing.
e	ession 2	Ssion 2  3 to 5 weeks after Experimental Session 1 (V5); at least 2 weeks after Integrative Session 1.3 (V9)  21 to 35 days after Experimental Session 1 (V5)  At least 14 days after Integrative Session 1.2

Integrativ Session 2 (Visit 11)		V11 is a 90-minute Integrative Session the morning after V10. Followed by 4 phone check-ins over 7 days post V10.
Integrativ Session 2 (Visit 12)		Approximately 2 weeks after V10, a 90-minute Integrative Session (V12) is completed.
	after Integrative Session 2.1 (V11)	
Integrativ Session 2 (Visit 13)	e 1.5 hours/	90-minute Integrative Session post V12. Measures include LEC-5, PCL-5 and Since Last Visit C-SSRS.
	20 to 34 days after Experimental Session 2 (V10); at least 2 days after Integrative Session 2.2 (V12)	

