## Follow-up Period and Study Termination

From Integrative Session 2.3 (Visit 13) until Study Termination (Visit 15): 4 weeks (+/-2). After Integrative Session 2.3 (Visit 13), ~4 weeks with no scheduled study visits until the Primary Outcome is completed.

	Outcome is completed.				
Study Visit/		Visit Duration/	Brief Description of Events		
Visit #		Visit Timing/			
		(Scheduling Window)			
Primary Outcome	Primary Outcome CAPS-5 T3 (Visit 14)	1 hour/ ~13 (+/-3) weeks after Baseline CAPS-5 T1 (V3) & 8 weeks (+/-2) after Experimental Session 2 (V10)  67 to 112 days post Baseline CAPS-5 T1 (V3); 42 to 70 days after Experimental Session 2 (V10)	Primary Outcome CAPS-5, SDS, and DSP-I assessment completed by an IR via tele-assessment. Although there are allowable windows for all visits throughout the protocol, this visit must be completed within the overall window. Other visits should be scheduled to ensure the timing of the Primary Outcome CAPS-5 T3 assessment is appropriate.		

Termination	Study Termination (Visit 15)	2 hours ~13 (-3/+4) weeks after Baseline CAPS-5 T1 (V3) & 2 days (-1/+7 days) after Primary Outcome	Complete self-reported and safety measures; create an exit plan for participant.
erm		CAPS-5 T3 (V14)	
Study		68 to 121 days after	
$\sim$		Baseline CAPS-5 T1	
		(V3); 1 to 9 days after	
		Primary Outcome	
		CAPS-5 T3 (V14)	

Qualified IRs selected based on availability from the IR Pool will perform the CAPS-5 assessments as described Table 2.

Table 2: Primary Outcome (CAPS-5) Data Collection by Visit

CAPS Administration	Visit	Description/Timing	Target Timing Post Baseline (V3)
Baseline CAPS-5 T1	V3	Baseline; between V2 and confirmation of end of tapering and stabilization of medications	0 days
CAPS-5 T2	V8	Post Experimental Session 1 (3 weeks -3/+9 days); between Integrative Sessions 1.2 and 1.3 (V7 & V9)	~6 weeks
Primary Outcome CAPS-5 T3	V14	Post Experimental Session 2 (8 weeks +/-2) after Experimental Session 2 (V10); after Integrative Session 2.3 (V13) (4 weeks +/-2).	~13 weeks

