## 4.2 Planned Duration of Study

Full screening may take 2 to 6 weeks after completion of phone screening, where performed. The Preparatory Period begins at enrollment and can be as brief as 2 weeks. Depending on medication tapering could be as long as 11 weeks to ensure an appropriate medication washout of at least five half-lives of pre-study psychiatric medications and active metabolites, and at least one additional week for stabilization.

Enrollment Confirmation takes place at the completion of the Preparatory Period, at which time the Treatment period will commence. The approximate 8-week Treatment Period will consist of two Experimental Sessions 3 to 5 weeks apart with associated non-drug Integrative Sessions and CAPS-5 assessment.

After the final Integrative Session 2.3 (Visit 13), participants will enter follow-up with no study visits for approximately 4 weeks, after which the Primary Outcome CAPS-5 T3 assessment will take place (Visit 14). Although there are allowable windows for all visits throughout the protocol, the overall timelines should comply with the target timing of the Primary Outcome CAPS-5 T3 assessment, which must be completed 13 weeks (+/-3 weeks) post Baseline, even if the maximum possible visit windows were used between visits. Other visits should be scheduled to ensure the timing of the Primary Outcome CAPS-5 T3 assessment is appropriate. The Study Termination visit follows 1 to 9 days after the final CAPS-5 assessment.

The minimum time that a participant who completes all study visits from Screening to Study Termination will be in the clinical trial is 14 weeks and the maximum is 27 weeks. The average participant is expected to complete the study in 17 weeks. Any delays between visits outside of the protocol-defined windows may result in a corresponding extension of study duration and should be documented as a deviation as appropriate.

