Table 6: Time and Events – Treatment and Follow-up Period

	Treatment Period ~8 weeks (+/-3 weeks)										Follow-up Period & Study Termination (~4 weeks) 13 weeks (+/-3 weeks) post baseline		
			Treatmen	t 1			Treat	Primary	Study				
Visit	V5	V6	V7	V8	V9	V10	V11	V12	V13	Outcome V14	Termination V15		
Visit Description	Exp. 1	Int. 1.1	Int. 1.2	CAPS-5 T2: Tele- assessme nt	Int. 1.3	Exp. 2	Int. 2.1	Int. 2.2	Int. 2.3	CAPS-5 T3 Outcome: Tele- assessment A	Study Termination		
Visit Timing	Within 1 week of V3	Mornin g after V5	3 to 14 days after V5	18 to 30 days after V5	20 to 34 days after V5	21 to 35 days after V5	Morning after V10	3 to 14 days after V10	20 to 34 days after V10	13 weeks post V5 (+/-3 weeks)	2 days post V14 (-1/+7 days)		
Concomitant medication review	✓	✓	✓		✓	✓	✓	✓	✓		✓		
Symptom-directed Physical Exam	√					√					√B		
Drug Test C	✓					✓							
Pregnancy Test D	✓					✓			✓				
Digital Recording of Visit	✓	✓	✓	✓	✓	✓	✓	✓	✓	✓			
AE Assessment E	✓	✓	✓		✓	✓	✓	✓	✓		✓		
Administer IP	✓					✓							
8-hour Exp. Session	✓					✓							
Blood Pressure, Pulse, Temperature F	✓					✓					✓		
Overnight Stay	✓					✓							
90-min Integrative Session		✓	✓		✓		✓	✓	✓				
Phone Call Follow-up G	1.1.1.	✓	1 0		DG 5 FD		✓ /	11 . 1	:1.1.12	1 (1/2 1)	175		

A All visits must be scheduled to ensure that the Primary Outcome CAPS-5 T3 assessment is within the overall window provided: 13 weeks (+/-3 weeks) post V5

B At Study Termination, includes weight. A symptom-directed physical exam to be conducted only if clinically indicated.

<sup>C In the UK, also includes testing for alcohol. Must be completed prior to IMP dosing.

<sup>D PABP only. At Visit 5 and Visit 10, a negative urine pregnancy test must be confirmed prior to IMP dosing.

<sup>E Adverse Events (Aes) Assessment includes collecting Serious Adverse Events, Aes of Special Interest, Aes of Psychiatric Status, Aes requiring medical advice or attention, Aes that indicate withdrawal of a participant, and all other Aes.

F During Experimental Sessions, vitals are measured before Investigational Product administration, immediately before the supplemental dose is administered (or would be, if supplemental dose not given), approximately 8 hours after initial dose, and as needed.

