#### 7.3.3 Integrative Sessions

After each Experimental Session, three Integrative Sessions will take place. Each session will consist of 90 minutes of psychotherapy.

#### Treatment 1

- Integrative Session 1.1 (Visit 6): morning after Experimental Session 1 (Visit 5)
- Integrative Session 1.2 (Visit 7): 3 to 14 days after Experimental Session 1 (Visit 5) and at least 2 days after Integrative Session 1.1 (Visit 6)
- Integrative Session 1.3 (Visit 9): within 3 to 5 weeks after Experimental Session 1 (Visit 5) and 1 to 7 days in advance of Experimental Session 2 (Visit 10). At least two days after Integrative Session 1.2 (Visit 7). This visit serves two purposes: to continue integration and to prepare for the next Experimental Session. The participant will complete the LEC-5 and PCL-5 self-report measures.

#### Treatment 2

- Integrative Session 2.1 (Visit 11): morning after Experimental Session 2 (Visit 10)
- Integrative Session 2.2 (Visit 12): approximately 2 weeks after Experimental Session 2 (Visit 10)
- Integrative Session 2.3 (Visit 13): within 3 to 5 weeks of Experimental Session 2 (Visit 10). This visit serves to continue integration. The participant will complete the LEC-5 and PCL-5 self-report measures. For PABP, a final urine pregnancy test will be conducted at this visit, Visit 14 or Visit 15 (representing the end of the relevant systemic exposure, 5 half-lives after the last IMP dose, and at least 2 weeks after the last MDMA experimental session).

During Integrative Sessions, the therapy team will:

- Record the session.
- Inquire about any possible changes in health. Assess the participant's mental health and the status of any previously recorded AEs. Record AEs as described in Section 10.0 Safety.
- Inquire about concomitant medication use and adherence.
- Administer Since Last Visit C-SSRS to determine suicidal risk.
- Discuss and review events that occurred with the participant during the Experimental Session, including thoughts, feelings, and memories. If necessary, the therapy team will help the participant to reduce any residual psychological distress they are experiencing. The therapy teams will also encourage the transfer of states of acceptance, feelings of intimacy, closeness, and reduced fear experienced in Experimental Sessions to emotionally threatening everyday situations. The therapy teams will be supportive, validate the experience, and facilitate understanding and emotional clearing.

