#### 7.4.3 Study Termination

Study Termination (Visit 15) will take place 2 (-1/+7) days after the final CAPS-5 assessment (Visit 14). Participants who have withdrawn from treatment but have continued for follow-up will also complete this assessment immediately upon withdrawal.

The site team will:

- Inquire about any possible changes in health. Assess the participant's mental health and the status of any previously recorded AEs. Record AEs as described in Section 10.0 Safety.
- Inquire about concomitant medication use and adherence.
- Administer Since Last Visit C-SSRS.
- Conduct symptom-directed physical examination if clinically indicated.
- Conduct pregnancy test (at Visit 13, 14 or 15, or earlier if early withdrawal).
- Measure weight (used to calculate BMI).
- Measure blood pressure.
- Provide and discuss a study exit plan.
- Actively support participant in completion of Study Termination self-reported measures:
  - o LEC-5
  - o PCL-5, ensure assessment is in relation to index trauma
  - o BDI-II
  - o CPGS
  - o EO-5D-5L
  - o SCS
  - o AUDIT
  - o DUDIT
  - o SRNU
  - o EAT-26

Completion of the measures do not need to be recorded.

After all Study Termination measures and assessments are completed, the participant is considered terminated from the study. The participant can resume normal everyday life. The study team will provide an Exit Plan, which may include a referral for additional medical or therapeutic care, as described in Section 7.4.4 Exit Plan. Eligible participants will be asked whether they are interested in participating in the LTFU extension study.

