## 10.3.3 Follow-up Requirements

Details of all pregnancies in study participants will be collected after Enrollment (Visit 0) and collected through 10 days after the last Experimental Session. Pregnancies should be reported to the sponsor via telephone or email within 24 hours of site staff awareness.

In the event of a pregnancy, the participant will discontinue Experimental Sessions but may continue with non-drug Integrative Sessions, the next CAPS-5 assessment, and Study Termination procedures. At a minimum, prior to withdrawal from the study, efforts should be made to assess the final CAPS-5 immediately and complete Study Termination procedures.

The investigator will collect follow-up information on the participant and neonate and forward to the sponsor until the outcome of the pregnancy, which will be reported in the Pregnancy eCRF. Any termination, elective or spontaneous, will be reported. Abnormal pregnancy outcomes, such as spontaneous abortion, fetal death, stillbirth, congenital abnormalities, or ectopic pregnancy, will be reported as SAEs.

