## 12.0 Clinical Laboratory Assessments

The site physician will confirm laboratory assessments gathered in screening for assessing eligibility. The site physician will use a list of normal ranges to conclude whether participants are eligible for the protocol and will indicate justification for admitting participants with abnormal values after consultation with the Medical Monitor.

The following laboratory assessments will be performed as a part of Screening:

- Serum electrolytes and metabolic profile
  - o Alanine aminotransferase (ALT)/serum glutamic pyruvic transaminase (SGPT)
  - o Albumin:globulin (A:G) ratio
  - o Albumin, serum
  - o Alkaline phosphatase, serum
  - Aspartate aminotransferase (AST)/serum glutamic oxaloacetic transaminase (SGOT)
  - o Bilirubin, total
  - o Blood urea nitrogen (BUN):creatinine ratio
  - o Calcium, serum
  - Carbon dioxide
  - o Chloride, serum
  - o Creatinine, serum
  - Globulin, total
  - o Glucose, serum
  - o Potassium, serum
  - o Protein, total, serum
  - o Sodium, serum
- CBC
  - Hematocrit

- o Hemoglobin
- Mean corpuscular volume (MCV)
- o Mean corpuscular hemoglobin (MCH)
- o Mean corpuscular hemoglobin concentration (MCHC)
- o Red cell distribution width (RDW)
- Percentage and absolute differential counts
- o Red blood cell (RBC) count
- White blood cell (WBC) count
- Urinalysis
  - Color
  - o Appearance
  - o Specific gravity
  - о рН
  - o Protein
  - o Glucose
  - Ketones
  - Occult blood
  - Leukocyte esterase
  - Nitrite
  - Bilirubin
  - Urobilinogen
- Thyroid function
  - Thyroid-stimulating hormone (TSH) high sensitivity (if abnormal, free T3 and T4 will also be tested)
- HCV antibody if indicated, with reflexive RNA test
- %Carbohydrate deficient transferrin (%CDT) to detect heavy alcohol use
- Pregnancy test
  - o A highly sensitive pregnancy test for PABP will be performed at the site or by the central lab at screening, and at the site before each experimental session.
  - A serum or urine sample may be used.
    - In the UK, screening pregnancy test must use serum only.
  - o A final urine pregnancy test should be completed at Visit 13 (or at Visit 14 or 15, if Visit 13 is done remotely) for PABP.
- Qualitative drugs test
  - O To be performed at the site during screening and before each experimental session.
    - In the UK, also includes alcohol.

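### Section 10.3.3 stops collecting pregnancy details at day 10 after the last Experimental Session, but the final scheduled pregnancy test comes on day 20 or later

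*Protocol*

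**What the plan says.** **Collection window.** Section 10.3.3 starts collecting pregnancy details after Visit 0, and they are "collected through 10 days after the last Experimental Session". The same section asks for a report to the sponsor within 24 hours of site awareness, follow-up to the outcome of the pregnancy, and SAE reporting of abnormal outcomes.

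**Testing schedule.** In the treatment and follow-up table (Table 6), pregnancy tests are marked at Visits 5, 10 and 13 only. Footnote D covers the two dosing visits: "At Visit 5 and Visit 10, a negative urine pregnancy test must be confirmed prior to IMP dosing". Three sections place the last test:

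- Section 12.0: "A final urine pregnancy test should be completed at Visit 13 (or at Visit 14 or 15, if Visit 13 is done remotely" for participants able to become pregnant.
- Section 7.3.3: Visit 13, 14 or 15, described as "at least 2 weeks after the last MDMA experimental session" and as marking the end of relevant systemic exposure.
- Section 7.4.3: "Conduct pregnancy test (at Visit 13, 14 or 15, or earlier if early withdrawal".

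**Visit timing.** Table 1 puts Visit 13 at "20 to 34 days after Experimental Session 2 (V10" and Visit 14 at "42 to 70 days after Experimental Session 2 (V10". For Visit 15, section 4.2 states: "The Study Termination visit follows 1 to 9 days after the final CAPS-5 assessment".

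**What a positive test leads to.** Section 7.3.1.1 makes a positive pre-dose screen a reason to withdraw the participant from the protocol. Section 4.3.4 names pregnancy among the conditions that end Experimental Sessions while the participant stays for the associated Integrative Sessions. Section 10.3.3 allows Integrative Sessions, the next CAPS-5 and Study Termination procedures to continue.

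**The concern.** After the Visit 10 pre-dose test, the final test is the first scheduled check that could find a pregnancy exposed to MDMA at Session 2 but too early to show before dosing. Section 9.2.3.4 acknowledges that there are no clinical data on MDMA in pregnancy, so any exposed case is informative. The same section judges harm in early human pregnancy unlikely, so what is at stake is completeness of safety data rather than a known hazard.

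A site that takes day 10 as a limit on detection or reporting would have no stated duty under the collection sentence to record a positive final test. Collection should not depend on how a site reads one sentence.

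There is a related conflict. A site with a positive screen at Visit 10, after exposure at Visit 5, is told in one place to withdraw the participant and in another to keep them. Following 7.3.1.1 would lose later safety follow-up, as well as CAPS-5 data that SAP 8.2 would use in the supportive *de facto* analysis.

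**Working it through.** The plan states no figure for this gap, so the check is day arithmetic on the protocol's own windows.

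**The windows are consistent with one another.** From Baseline (Visit 3), Visit 5 is 4 to 7 days later, Visit 10 is 21 to 35 days after Visit 5, and Visit 14 is 42 to 70 days after Visit 10.

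- Visit 14 earliest: 4 + 21 + 42 = 67 days. Latest: 7 + 35 + 70 = 112 days. Table 1 gives 67 to 112.
- Visit 15 adds 1 to 9 days: 67 + 1 = 68 and 112 + 9 = 121. Table 1 gives 68 to 121.

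**Gap between the day-10 limit and the final test.** Day 0 is Experimental Session 2 (Visit 10), with both sessions completed. Gap = test day − 10.

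| Final test at | Test day | Days after the limit |
|---|---|---|
| Visit 13 (default) | 20 to 34 | 20 − 10 = 10 to 34 − 10 = 24 |
| Visit 14 | 42 to 70 | 42 − 10 = 32 to 70 − 10 = 60 |
| Visit 15 | 42 + 1 = 43 to 70 + 9 = 79 | 43 − 10 = 33 to 79 − 10 = 69 |

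Every permitted date is later than day 10, and the smallest gap is 10 days. With the default schedule there is no scheduled test for 20 to 34 days after the Visit 10 pre-dose test.

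**What each reading of day 10 does to a positive final test.**

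- *Detection or reporting by day 10:* no positive final test falls inside the window.
- *Conception by day 10:* a positive final test counts if estimated conception was by day 10, whenever it is found.

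Section 10.3.3 does not choose between them.

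**Positive pre-dose screen.** Section 7.3.1.1 does not distinguish Visit 5 from Visit 10. At Visit 5 no drug has been given, so withdrawal loses no exposed follow-up. At Visit 10 the participant received MDMA 21 to 35 days earlier, and 4.3.4 and 10.3.3 both provide for continued participation.

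**The case against.** The best counter-argument is that the intended meaning can be worked out. Section 7.3.3 ties the final test to the end of exposure. The half-life in section 1.2.2 is 7 to 9 hours, so five half-lives are 35 to 45 hours, and section 9.2.3.4 gives about 48 hours. Inclusion criterion 7 also ends contraception on day 10. On that view day 10 is an exposure limit with a margin, and the later test looks for conceptions within it. A final test whose positives were never recorded would have no purpose. The 24-hour reporting rule carries no end date. Abnormal outcomes are SAEs, and section 10.1.2 collects SAEs through Study Termination.

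Most of this stands and makes actual loss unlikely. It does not put the conception reading into 10.3.3. The SAE route covers only abnormal outcomes that occur by Visit 15, at the latest day 79.

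It can also be said that 10.3.3 is only permissive and itself anticipates withdrawal, so it can be reconciled with 7.3.1.1. That is fair. The clearer conflict is with 4.3.4, which names pregnancy and keeps the participant in the study, although its rule depends on a judgement by the Medical Monitor or site that safety is affected.

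Three stronger inferences are not supported:

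- **That exposed pregnancies will be lost.** The text is ambiguous; it does not establish loss of data.
- **That the final test could fall on day 14, only 4 days after the limit.** Section 7.3.3 allows the test only at Visit 13, 14 or 15, and Visit 13 is day 20 at the earliest.
- **That the differing contraception end dates prove the collection window wrong.** Inclusion criterion 7 (day 10), section 9.2.3.4 (one month after the last dose) and section 11.1 (after Study Termination) govern contraception, not data collection. Their disagreement is a separate inconsistency.

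**Conclusion.** The point holds as an ambiguity in a safety-collection rule. After two completed sessions, the final pregnancy test always falls after the day-10 limit: by 10 to 24 days at Visit 13 and by 32 to 69 days at Visit 14 or 15. Read by detection date, the rule excludes every positive result from that test. The conception-date reading is the more plausible intention but is not stated. The conflict over a positive Visit 10 screen is real and also needs resolving.

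The severity is minor. The documents give no pregnancy rate, and the expectation of few or no cases rests on the ceiling of 40 participants. The primary analysis is unaffected, because SAP 8.7.1 excludes CAPS-5 data collected after treatment discontinuation.

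The day counts assume that both sessions were given and that visits fall within their windows. Section 7.4.3 allows an earlier test at early withdrawal, which is outside this calculation.

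**What to change.** **Section 10.3.3.** Collect, and follow to outcome, all pregnancies detected from Visit 0 through Study Termination (Visit 15), including any positive final test. Add any pregnancy with estimated conception by day 10 after the last Experimental Session, whenever the site learns of it. Record timing relative to the last MDMA dose. The first part matches the AE collection period in section 10.1 (Visit 0 to Visit 15). The second is needed because a limit at Visit 15 alone would miss an exposed conception found later.

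**Section 7.3.1.1.** State that a positive screen at Visit 10 stops further dosing but leaves the participant in the study for Integrative Sessions, CAPS-5 and Study Termination procedures, in line with 4.3.4 and 10.3.3. A positive screen at Visit 5, before any dose, can remain cause for withdrawal.

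**Cost.** Wording in two sections, with no added tests or visits and no SAP change. A few unexposed late conceptions, up to day 79, would also be captured; the recorded timing would identify them. The contraception end dates would still need to be reconciled separately.

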#### 11.0 Concomitant Medications

## 11.1 Tapering Instructions

The site physician will record concomitant medications during Screening. If the prospective participant is being treated with psychiatric medications at enrollment, the prospective participant will be encouraged to discuss medication tapering with their outside treating physician, if any, and will be required to give the site physician permission to do so as well. The medications will then be tapered in an appropriate fashion to avoid withdrawal effects and discontinued at least five half-lives plus one additional week for stabilization before the first Experimental Session to avoid the possibility of any interaction. Additionally, participants who are taking prohibited opiates will be cross-tapered to an allowable opiate (hydrocodone, morphine, and codeine) under the care of their prescribing physician.

The site physician will consult the prescribing physician to initiate medication tapering for participants, as they must refrain from taking psychiatric medications throughout the study, with some exceptions (see Section 11.2 Allowable Concomitant Medications). The prescribing physician's opinion about medication discontinuation will documented either in writing from the prescribing physician, or in writing by the site physician documenting phone contact with the prescribing physician. Tapering will follow a time course appropriate for the medication based on its half-life, with the first Experimental Session scheduled to occur after complete washout (five half-lives plus at least 1 week for stabilization). If the health of the participant worsens after tapering, the participant will be withdrawn from the study and will be treated according to standard clinical practice. This will be recorded in the eCRF.

The therapy team will request information about any changes in medication at each contact. The site physician will be responsible for reviewing and confirming all medications collected during the study.

All medications, non-prescription and prescription, will be collected from Screening through 7 days after the last Experimental Session. From 7 days after the last Experimental Session through Study Termination, only prescription or non-prescription medications taken to treat AEs will be collected. Throughout the protocol, all medications used to treat AEs will be collected, and all changes including discontinuations or additions to medications will be collected. The study team will inquire and document all information about withdrawal and tapering of medications, concomitant medication and medication adherence in the eCRF Concomitant Medications.

Participants may return to taking psychiatric medications and discontinue birth control after the final Study Termination visit if necessary.

